## **D. Subject Criteria (See Vulnerable Populations appendix, if applicable):**

### **1. Inclusion criteria:**

Potential subjects must meet the following criteria at the screening visit to enter this study:

- Male or female, between the ages of 18 to 65 years
- Diagnosis of migraine, with or without aura, according to ICHD-2 criteria (Appendix A) for at least 1 year prior to screening; experience an average of 1 to 8 migraines per month.
- Females must be practicing an effective method of birth control before entry and throughout the study, or be surgically sterile, or be postmenopausal
- Females of child-bearing potential must have a negative urine pregnancy test
- Subjects should be able to demonstrate the ability to properly administer study medication
- Subjects should be able and willing to read and comprehend written instructions and complete the diary information required by the protocol
- Subjects must be capable, in the opinion of the Investigator, of providing informed consent or assent to participate in the study
- Subjects (and their legally acceptable representatives, if applicable) must provide an informed consent indicating that they understand the purpose of and procedures required for the study and are willing to participate in the study

### **2. Exclusion criteria:**

Potential subjects who meet any of the following criteria will be excluded from entering this study:

- Inability to distinguish other headaches from migraine
- Experiences headache of any kind at a frequency greater than or equal to 15 days per month
- Current use of medication for migraine prophylaxis that has not been stable (no dose adjustment) for 30 days prior to screening
- Chronic opioid therapy for headaches (> 3 consecutive days in the 30 days prior to screening)
- Hemiplegic migraine
- History, symptoms or signs of ischemic cardiac, cerebrovascular or peripheral vascular syndromes. Ischemic cardiac syndromes include, but are not limited to, angina pectoris of any type (e.g., stable angina of effort, vasospastic forms of angina such as the Prinzmetal variant), all forms of myocardial infarction and silent myocardial ischemia. Cerebrovascular syndromes include, but are not limited to, strokes of any type as well as transient ischemic attacks. Peripheral vascular disease includes, but is not limited to, ischemic bowel disease, Raynaud syndrome
- History of glaucoma and/or current treatment with prescription eye drops
- History of naso-lacrimal duct ("tear duct problem" to patients) obstruction or surgery for such
- Active treatment by ophthalmologist or optometrist for any severe ophthalmic disease or problem
- Any physical problems or co-ordination difficulty or eye avoidance sensitivity ("squeezer") that would preclude proper installation of eye drops in either or both eyes
- History of uncontrolled asthma, COPD, or reversible airway disease which in the opinion of the investigator would be worsened by the use of beta blockers
- History of clinically symptomatic bradycardia, congestive heart failure, or hypotension
- Uncontrolled Diabetes Mellitus
- Uncontrolled Hyperthyroidism

- History (within 2 years) of drug or alcohol abuse as defined by DSM-IV criteria
  - Systemic disease, which in the opinion of the Investigator, would contraindicate participation
  - History of a neurological or psychiatric condition, which in the opinion of the Investigator would contraindicate participation
  - History of hypersensitivity or intolerance to beta-blockers eye drops
  - Pregnant or lactating women
  - Have taken any investigational medication within 12 weeks before randomization, or are scheduled to receive an investigational drug
  - Subjects, who in opinion of the Investigator, should not be enrolled in the study because of the precautions, warnings or contra-indications sections of the timolol Package Insert
3. Withdrawal/Termination criteria: Although we do not anticipate any adverse events, subjects who experience any adverse effect from the study drug will be withdrawn from the study. Since the study drug will be used only once there will be no need to taper the drug dose. There wont be any tests necessary upon withdrawal from the study. Also, subjects who do not have any migraines attacks in the given 8 weeks period will be dropped from the study.
4. The study subject will not participate in another research study while participating in this study.

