F. Subjects who meet all inclusion and exclusion criterion will be identified and recruited through routine office visits. Subjects will be randomized in a double-blinded fashion to either the study medication arm or placebo arm. They will be sent home with one bottle of the drug, which will be either the study medication (0.5% timolol ophthalmic solution) or the placebo (0.9% normal saline solution). They will be provided instructions on proper administration of the eye drops. They will treat their first migraine attack with 1 drop of ophthalmic solution in each eye (either study medication or placebo, depending upon which study arm they are in). If they miss the eye in the first attempt, they may re-administer another drop. They will be asked to then blink rapidly for 3-5 seconds to promote absorption. After 15 minutes, if the migraine headache is still present, they can re-administer one drop in each eye. They will record their migraine pain level using the comparative pain scale (Appendix B) before administering the eye drops and 2 hours after treatment. They will also report their treatment satisfaction using the forms provided (Appendix C). After the treatment of their first migraine attack, the subjects will notify the study staff and will either come in to return the first bottle and forms or they will send in their medications and forms. Once the first bottle is received, we will either mail in using a service like FedEx or they will return to pick up their second bottle. At the interim visit, if the subjects decide to return their first bottle via mail, they will be contacted by the study staff via phone call, in order to report any changes in their concomitant medications or any adverse events. The subjects will treat their second migraine attack with the second drug and again report their migraine pain level using the comparative pain scale and also report treatment satisfaction. See table below.

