**Table 1: Schedule of events**

Procedure	Baseline Visit	Interim Visit	End of Study Visit
Consent	X		
Demographics	X		
Medical History	X		
Concomitant Medications	X	X	X
Physical Exam	X		X
Vital signs	X		X
Urine pregnancy screen	X		X
Drug Dispensing	X	X	
Drug Accountability		X	X
Adverse events		X	X
Pain Questionnaire	X	X	X
Satisfaction Questionnaire	X	X	X
Data Entry	X	X	X

At any point, during the treatment of their migraine attacks with the study medications, rescue medications (like NSAIDs, triptans or their usual migraine abortive medications) can be taken 120 minutes after the study drug dose, if necessary. After treating their second migraine attack, the subjects will return for an end-of-study visit. This should occur within 7 days after treating their last qualifying migraine, or after 8 weeks of enrolling in the study (whichever comes first). The subject's diary information will be reviewed and all end-of-study visit procedures will be performed

Subjects will use a diary to collect all attack and safety data needed for data analysis. They will use the comparative pain scale to grade their migraine pain level before and at 2 hour after administration of study ophthalmic drops. They will be provided forms during each visit to record their pain score and treatment satisfaction. A safety monitor will be appointed and all adverse reactions will be reported, although we do not anticipate any adverse events given the short duration of the study and established safety of the drug. All data collected from the patients will be entered on a secured spreadsheet/ database. No patient identifiers will be used. Descriptive statistics will establish baseline characteristics and adverse event frequency. Data for the primary endpoint will be statistically analyzed via 2-tailed t-test. Data for the secondary outcome measures will be statistically analyzed for both within and between group changes via 2-tailed repeated measures ANOVA and or independent or dependent t-tests as appropriate. All ANOVAs will be followed by univariate post-hoc tests.

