**L. Assessment of Subject Safety and Development of a Data and Safety Monitoring Plan**

1. Elements of the plan include:
  - a. Persons/groups who will review the data (study team; independent safety monitor, data monitoring committee or formal DSMB) Study personnel
  - b. Data/events that will be reviewed - All collected data will be reviewed
  - c. Frequency of review - Once a month
  - d. Types of analyses to be performed
  - e. Safety-related triggers that would cause the PI to stop or alter the study  
We do not anticipate any safety related triggers that would cause the study to be stopped or altered
2. We do not anticipate any adverse events in the study. In case of any unanticipated problems we will have a safety monitor appointed for the study. Any adverse event from the drug will be treated in timely fashion. The subject will be withdrawn from the study in case of any adverse events.
3. The subject will be withdrawn from the study in case of any adverse events to ensure safety.

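### Any adverse effect, however mild, ends participation: an effect in attack one costs the second-attack scores, and it is unclear whether a withdrawn subject has the exit vital signs and exam

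*Combined protocol and SAP*

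**What the plan says.** **The withdrawal rule.** Section II.D item 3 (Withdrawal/Termination criteria) states that "subjects who experience any adverse effect from the study drug will be withdrawn from the study", and adds: "There wont be any tests necessary upon withdrawal from the study". Section II.L states the rule in items 2 and 3, the latter reading: "The subject will be withdrawn from the study in case of any adverse events to ensure safety". Neither section sets a severity threshold. II.D limits the trigger to effects of the study drug; II.L item 3 does not.

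**The design it acts on.** Under Section II.B item F, each subject treats one attack with bottle one, returns it, and only then receives bottle two for the second attack. Subjects who return bottle one by mail are "contacted by the study staff via phone call, in order to report any changes in their concomitant medications or any adverse events". Section II.C caps enrolment at 26. No replacement or missing-data rule is given.

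**Exit assessments.** Table 1 places vital signs and physical exam at baseline and end of study only. The text after the table says: "After treating their second migraine attack, the subjects will return for an end-of-study visit". It then times that visit within 7 days of the last qualifying migraine or after 8 weeks from enrolment, whichever is first.

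**Other safeguards.** Section II.B says "A safety monitor will be appointed and all adverse reactions will be reported". Section II.L item 2 says "Any adverse event from the drug will be treated in timely fashion", and item 1 provides for monthly data review.

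**The concern.** A crossover needs both scores from each subject, and the second exists only if bottle two is released. A rule that stops the subject for transient stinging removes that score because of how the first bottle was tolerated, so the missingness is informative rather than incidental. It need not be balanced. A timolol-first withdrawal removes a saline score; a saline-first withdrawal removes a timolol score and a timolol exposure. If timolol causes more effects than saline, a paired comparison leans on subjects who tolerated timolol first. The second satisfaction score, part of the secondary endpoint in Section V.B, goes as well. An effect in attack two costs no score, provided the 2-hour value is recorded.

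Specific Aim 2 is safety and tolerability. Subjects who reacted to bottle one are the ones for whom an objective exit assessment is most useful, and the plan does not say clearly that they have one.

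**Working it through.** **1. The plan's own figure.** Section II.B states 26 subjects for 90% power at the 5% level, 25% against 65%. Using the two-sided two-proportion formula with unpooled variance, per treatment condition:

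n = (1.960 + 1.282)² × (0.25×0.75 + 0.65×0.35) / 0.40² = 10.51 × 0.415 / 0.16 = 27.3, so 28.

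Power at 26 per condition = Φ(0.40/√(0.415/26) − 1.960) = Φ(1.206) = 88.6%.

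The figure is roughly reproduced if each crossover subject counts once on each treatment. It carries no allowance for withdrawals. It concerns a binary outcome, whereas the primary test is a two-tailed t-test, not stated to be paired or unpaired. Below, 90% at 26 is therefore only a reference point set for the t-test, to show relative loss.

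**2. Scores lost.** Let r be the first-attack adverse-effect rate on either drug (assumed; none is given). Expected second-attack scores lost = 26r. Subjects ever exposed to timolol = 26 − 13r, assuming 13 per sequence, because only saline-first withdrawals lose a timolol exposure.

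**3. Power.** Two-sided 5% noncentral t. A standardised difference of 0.662 gives 90% with 26 pairs; 0.917 gives 90% with 26 against 26 unpaired. Unpaired analysis keeps the first score of a withdrawn subject, so each treatment retains 26 − 13r scores.

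| Assumed r | Second scores lost | Pairs left | Power, paired | Scores per treatment, unpaired | Power, unpaired | Timolol exposures |
|---|---|---|---|---|---|---|
| 5% | 1.3 | 24.7 | 88.3% | 25.35 | 89.2% | 25.35 |
| 10% | 2.6 | 23.4 | 86.4% | 24.7 | 88.4% | 24.7 |
| 20% | 5.2 | 20.8 | 81.8% | 23.4 | 86.6% | 23.4 |

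**4. Unequal rates.** With 20% on timolol and 5% on saline (assumed), timolol-first subjects lose 13 × 0.20 = 2.6 saline scores and saline-first subjects lose 13 × 0.05 = 0.65 timolol scores. That leaves 26 − 3.25 = 22.75 pairs, power 85.4%. Unpaired, 25.35 timolol against 23.4 saline scores give 87.9%.

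**5. Possible shift.** If the timolol-minus-saline difference in withdrawn subjects departs from that in the others by D points, the complete-pair mean departs from the all-subject mean by r × D. With D = 2 (assumed), the shift is 0.1, 0.2 and 0.4 points at r = 5%, 10% and 20%. This shows the mechanism; it is not an estimate.

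**6. Exit assessments, text against text.**
- Against an exit exam: II.D item 3 says no tests are needed on withdrawal, and the sentence introducing the end-of-study visit places it after the second attack. The interim contact may be by phone, and Table 1 schedules no vital signs or exam there.
- For an exit exam: Section III.E calls the urine dipstick the only test done for the study, so tests in II.D may mean just that. The 7-day clause runs from the last qualifying migraine, which for a one-attack subject could be the first attack. Nothing expressly cancels the visit.

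Both readings are open. The defect is ambiguity.

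**The case against.** Stopping on any drug effect is a defensible, conservative choice for unsupervised home use of a blinded beta-blocker in a small pilot. The stated purpose in II.L is safety, and the rule can spare a saline-first subject who reacted from then taking timolol. That stands as a reason to keep mandatory withdrawal for effects that matter; it does not require withdrawal for trivial ones.

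A reader might infer that the plan waives vital signs and examination for withdrawn subjects, or that their safety data are lost. The documents do not support either inference. The dipstick reading of tests and the 7-day clause both leave room for an exit visit. Adverse events and the first-attack pain and satisfaction forms are still collected at the interim contact, and drug events are to be treated. What is at risk is an objective assessment, which even for completers may come up to 7 days after the attack.

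A reader might also take II.L to withdraw subjects for wholly unrelated events. Item 3 can be read that way, but the withdrawal sentence in item 2 directly follows one about events from the drug, so this is arguable.

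Finally, the size rests on assumptions throughout. The sponsor anticipates no adverse events, and the 90% reference is borrowed: a McNemar calculation on the plan's 25% and 65% gives 80.5% at 26 pairs if responses are independent within subject. This is why the power figures show only relative loss.

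The option of a repeat drop at 15 minutes is not shown to be at fault by any of this.

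**Conclusion.** The point holds as a minor one. A stated rule without a severity limit makes second-attack scores missing for tolerability reasons in a 26-subject crossover whose second aim is tolerability, and the exit assessment of a subject withdrawn at the interim contact is left unclear. At assumed rates of 5% to 20% the loss is 1.3 to 5.2 second scores, or about 2 to 8 points of power paired and 1 to 3 unpaired, against a 90% reference taken at face value. That is modest. Loss that is unequal by sequence is possible, but the documents supply neither an adverse-effect rate nor a score difference from which to call bias likely.

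**What to change.** - **II.D item 3 and II.L items 2 and 3:** use one rule. Withdrawal is mandatory only for a drug-related effect that the investigator judges clinically important, for example bronchospasm, symptomatic bradycardia or hypotension, or hypersensitivity. The investigator decides at the interim contact, before bottle two is released. A subject with a lesser effect may continue if willing.
- **II.D item 3:** replace the sentence about tests with a statement that any withdrawn subject has the planned end-of-study vital signs and physical exam promptly, within 7 days of the treated attack.
- **Reporting:** give withdrawals by sequence and show withdrawn subjects' first-attack scores beside the main comparison.

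**Cost:** wording in two sections and an earlier end-of-study visit for a few subjects, already paid at $25 (Section III.G). No new subjects, forms or endpoints. The downside is that the investigator must grade effects under blinding, and some saline-first subjects with a mild effect will go on to timolol.

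Section II.C item 4 already reports results. For this trial the reporting step is therefore what can still be done; the wording would serve the larger studies the pilot is meant to lead to.

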#### **E. Specific methods and techniques used throughout the study**

##### 1. Laboratory test:

The subjects will be identified and enrolled from the neurology office visits. Once identified, they will be consented. Since they will be enrolled from the office visit, most data points like medical history, concomitant medications, vital signs and physical examination will not be repeated as this will be collected as a part of their neurology office visit. A urine pregnancy screen will be performed in female subjects in the childbearing age groups to ensure that they are not pregnant. Once enrolled, they will then be randomized in a double blind fashion into a study drug arm or placebo arm. They will be demonstrated on how to instill eye drops and will be sent home with one bottle of the drug with instructions to treat their migraine attack with the drug (either the study medication or placebo, based on their randomization). They will treat their first migraine attack with the drug and record their migraine pain level using the comparative pain scale and treatment satisfaction score using the satisfaction scale. All the scoring forms will be provided to them at their visit. After the treatment of their first migraine attack, they will return the drug bottle (either in person or via mail). They will then receive the second bottle (either in person or via FedEx) and will be instructed to treat their second migraine attack with the drug. They will again rate their migraine pain score using the comparative pain scale and the treatment satisfaction score using the satisfaction scale. Subjects will then return for an end of study visit. Vital signs, physical examination,

and a repeat urine pregnancy screen (in child bearing age group female subjects) will be obtained and recorded. The urine pregnancy screen will be done using a urine dipstick method. No specimens will be stored. All data collected will be entered on a secured spreadsheet/ database.

**Table 1: Schedule of events**

Procedure	Baseline Visit	Interim Visit	End of Study Visit
Consent	X		
Demographics	X		
Medical History	X		
Concomitant Medications	X	X	X
Physical Exam	X		X
Vital signs	X		X
Urine pregnancy screen	X		X
Drug Dispensing	X	X	
Drug Accountability		X	X
Adverse events		X	X
Pain Questionnaire	X	X	X
Satisfaction Questionnaire	X	X	X
Data Entry	X	X	X

**F. Risk/benefit assessment:**

1. Physical risk

We do not anticipate any physical risk to the study subjects. A safety monitor will be appointed in case of any adverse events.

2. Psychological risk

The study subjects may not have adequate pain relief with the study drug and the placebo. To minimize this risk, at any point during the treatment of their migraine attacks with the study medications, rescue medications (like NSAIDs, triptans or their usual migraine abortive medications) can be taken 120 minutes after the study drug dose, if necessary.

3. Social risk

We do not anticipate any social risk.

4. Economic risk

Study subjects will be enrolled from their usual office visits. However, for the interim (if they decide to return to pick up the second drug) and end of study visit they will be compensated with a nominal subject honorarium amount which may not be enough to cover their travel expense if they live far off.

5. Potential benefit of participating in the study

- a. The individual subject participating in the study will benefit from the treatment if the study drug is effective in aborting their migraine attack and provide pain relief.
- b. If the study drug is efficacious and safe in treating migraine headaches in study subjects, the medication can potentially be used for migraine patient population from which the subjects are drawn.
- c. If successful this pilot study will open doors for future trials and larger studies that will be able establish the use of beta blocker eye drops which is a simple and low cost acute treatment of migraine.

**G.**

**G. Location where study will be performed:** Neurology clinics located at Landon Center of Aging, [name]; Indian Creek Neurology Clinic located at [name] and the Spine Center Neurology Clinic located at [name].

**H. Collaboration (with another institution, if applicable):**

**I. Single IRB Review for a Multi-site study (if applicable)**

1. For which sites will KUMC serve as the IRB of record?  
Neurology clinics located at Landon Center of Aging, [name]; Indian Creek Neurology Clinic located at [name] and the Spine Center Neurology Clinic located at [name]
2. Indicate which study activities will occur at each site. If all study procedures will be identical across study sites, state this.  
Subjects who meet all inclusion and exclusion criterion will be identified and recruited through routine office visits at each of the above sites. They will be randomized in a double-blinded fashion to either the study medication arm or placebo arm.
3. Describe how you will assess the capacity of each site to perform the research (e.g., expertise, staffing, space, equipment, etc.) If applicable, include site evaluation tools in your IRB submission.  
Since the subjects will be identified and recruited through routine office visits, each of the above sites are fully equipped neurology clinics. The subjects will be identified and enrolled by physicians during the office visits. The clinic rooms, office ancillary staff and equipment will be used just like a regular neurology clinic visit.

4. Describe how the lead investigators will ensure that all participating sites use the IRB-approved version of the protocol, consent, recruitment materials and other study documents.  
We will make sure that all the participating sites and all study investigators are following the IRP protocol. Each site will have the protocol, consent forms, exam forms and other forms (pain scale and patient satisfaction scale).
5. Describe how the lead investigators will communicate with and disseminate new information to other sites (e.g., training meetings, regularly-scheduled conference calls, notifications, etc.)  
Routine meetings and /or conference calls will be conducted to communicate with all study personnel. Any new data or information pertinent to the study will be discussed during these meetings and phone calls.
6. Describe how the lead investigator will assess protocol compliance, unanticipated problems and adverse events at other sites.  
We do not anticipate any adverse events in this study. A safety monitor will be appointed for any adverse events, if any.
